5.5.3.4 Physical examination

A by-participant listing will be provided for physical examinations for the SS.

5.6 Subgroup analyses

Not Applicable.

5.7 Interim Analyses

There is 1 planned interim analysis. After completion of Part A, an interim analysis will be performed on key PK endpoints for all data, to support the decision on selection of the Part B formulation. Selected outputs flagged in the tables, listing, figure shells will be produced for the interim analysis.

5.8 Safety Monitoring Committee (SMC)

An SMC is planned for between Cohort 3 and Cohort 4 in Part B of the study to assess the safety data accumulated. This is set to take place once all participants of one ethnic group have completed Day 10 assessments. A detailed description of the composition and conduct of the SMC will be provided in a separate SMC Charter.

6 SUPPORTING DOCUMENTATION

6.1 Appendix 1 Non-key analysis specifications

6.1.1 Baseline characteristics and demographics

The body mass index (BMI) value collected in the eCRF will not be used for this summary. The BMI will be recalculated using the following formula and reported to 1 decimal place:

$$BMI(kg/m^2) = \frac{\text{body weight at screening (kg)}}{[\text{height at screening (m)}]^2} \quad (6)$$

6.1.2 Protocol deviations

Important protocol deviations (IPDs) are deviations from the protocol that potentially could have a meaningful impact on study conduct, safety, or PK outcomes for an individual study participant. Furthermore, study participants will be excluded from the Safety Set only when there is documented evidence that they received no treatment. The criteria for identifying IPDs and the classification of IPDs will be defined within the Protocol Deviation Assessment Plan. IPDs will be reviewed as part of the Data Cleaning Meeting and Data Evaluation Meeting (DEM). Any important deviation will be identified and documented before unblinding to confirm exclusion from analysis sets.

Protocol deviations will be classified as follows:

- AE SAE
- Disallowed medications
- Inclusion/Exclusion criteria
- Informed Consent

- Study treatment
- Other
- Procedures/tests
- Procedures/tests/lab
- Visit schedule
- Withdrawal criteria
- Time window deviation

The IPDs will be tabulated using the SS by study parts and sequence, and will present the deviation type.

6.1.3 Medical history

Medical history and ongoing medical conditions will be listed and summarized for the RS by study parts, treatment sequence, and for all participants by MedDRA SOC and PT. The reported term will be included in the listing. The summary will include the number and percentage of study participants and will be sorted alphabetically by SOC and by descending incidence of PT within each SOC, based on the 'All Participants' column.

6.1.4 Prior/concomitant medications

Medications with a start date prior to the first treatment will be considered as prior medications. Medications with a start date prior to, at or after the first treatment will be considered as concomitant medications if the duration overlaps at least 1 day with the any treatment period. Medications with a missing start date whose stop date is either unknown or after the date of the first treatment will be considered as concomitant.

Concomitant medications will be listed and summarized for the RS by study parts and treatment sequence, and will include WHODD (World Health Organization Drug Dictionary) Anatomical Main Group [Level 1 term text], Pharmacological Subgroup [Level 3 term text] and PT. The reported term will be included in the listing. Prior medications and concomitant medications will be summarized separately within the same table, ie, paged by prior and concomitant medications. Prior medications which continued into the study period are also classified as concomitant and are included in both summaries.

In the case of missing dates, the classification of medications as prior or concomitant will be performed after imputation of dates as described below. Imputations of missing dates will be performed prior to calculation of relative days.

The following rules are applied to impute partial start dates for medications:

- If only the month and year are specified and the month and year of first treatment is not the same as the month and year of the start date, then use the 1st of the month.
- If only the month and year are specified and the month and year of first treatment is the same as the month and year of the start date, then use the date/time of first treatment.
- If only the year is specified, and the year of first treatment is not the same as the year of the start date, then use January 1 of the year of the start date.

- If only the year is specified, and the year of first treatment is the same as the year of the start date, then use the date/time of first treatment.
- If the start date is completely unknown, then use the date/time of first IMP dose.

The following rules will be applied for partial stop dates and will be imputed for the calculation of duration of each medication:

- If only the month and year are specified, then use the last day of the month.
- If only the year is specified, then use December 31 of that year.
- If the stop date is completely unknown, do not impute the stop date.

Medications permitted to be continued during the study are limited to those listed in Section 6.5.1 of the protocol. No rescue medications are permitted.

All tabulations will be sorted alphabetically by Level 1 term, alphabetical Level 3 term within Level 1 and decreasing frequency of PT in the 'All Participants' column.

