#### **Prior/concomitant therapy**

11. Participant has received or intends to use any prescription or nonprescription medicines, including enzyme inhibitors or inducers, any gastric pH modifying agents, over the counter remedies, herbal and dietary supplements (including St. John's Wort) up to 2 weeks (4 weeks for enzyme inducers) or 5 half-lives of the respective drug (whichever is longer) before the first administration of study medication and during the clinical part of the study, unless required to treat an AE. Drugs with known CYP3A4 interaction (strong inducers and inhibitors) are prohibited. This does not include oral contraceptives exceeding 30µg ethinyl estradiol or postmenopausal hormone replacement therapy or implants, patches, or intrauterine devices (IUDs)/intrauterine hormone-releasing system (IUSs) delivering progesterone (for female study participants).

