5.5.2 Adverse Events

An Adverse Event is any untoward medical occurrence in a participant or clinical study participant, temporally associated with the use of study medication, whether considered related to the study medication.

Adverse events with start date/time prior to first treatment are defined as pre-treatment. These events will not be included in any tabulated summaries, but will be listed.

Treatment emergent AEs (TEAE) are all AEs starting on or after the date/time of first treatment and up to including 4 days after last treatment, or any unresolved event already present before administration of treatment that worsens in intensity following exposure to the treatment.

AEs with a start date after 4 days of last treatment are defined as post-treatment. These events will not be included in any tabulated summaries, but will be listed.

In case of missing or partially missing AE dates, the following rules will apply. Start and stop dates of AEs will be displayed as reported in the participant data listings (ie, no imputed values will be displayed in data listings).

The following rules will be applied for partial start dates and time:

- If only the month and year are specified and the month and year of the first treatment is not the same as the month and year of the start date, then use the 1st of the month, or the date of Screening if this is later (if the imputation results in an end date that is earlier than the start date, then use the 1st of the month). If time is missing, it will be imputed as 00:00 h
- If only the month and year are specified and the month and year of the first treatment is the same as the month and year of the start date, then use the date of the first treatment. If the imputed start date that is after the specified end date, then use the 1st of the month, or the date of Screening if this is later (if the imputation results in an end date that is earlier than the start date, then use the 1st of the month). If the imputed date is the date of treatment then time will be imputed as the start time of the treatment (ie, event will be regarded as treatment emergent)
- If only the year is specified, and the year of the first treatment is not the same as the year of the start date, then January 01 will be used. If time is missing, it will be imputed as 00:00 h

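### SAP 6.1.4 can impute a medication start date later than the stop date, so some medicines stopped before dosing count as neither prior nor concomitant

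*SAP*

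**What the plan says.** SAP 6.1.4 (Prior/concomitant medications) gives two definitions. For prior: "Medications with a start date prior to the first treatment will be considered as prior medications". A medicine is concomitant if its duration overlaps a treatment period by at least one day. One further sentence assigns a medicine with a missing start date to concomitant when its stop date is unknown or later than first treatment.

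The order of steps is fixed: "the classification of medications as prior or concomitant will be performed after imputation of dates as described below".

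The start-date rules that matter here are:

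- Month and year known, same as first treatment: "year of first treatment is the same as the month and year of the start date, then use the date/time of first treatment".
- Only the year known, same as first treatment: "the year of first treatment is the same as the year of the start date, then use the date/time of first treatment".
- Nothing known: "If the start date is completely unknown, then use the date/time of first IMP dose".

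Partial starts in another month or year are treated differently. For the month-and-year case: "year of first treatment is not the same as the month and year of the start date, then use the 1st of the month". For a year-only start in another year, 1 January of that year is used.

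Partial stop dates go to the end of the month or to 31 December. A wholly unknown stop date is left missing.

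SAP 5.5.2 (Adverse Events) uses the same kind of imputation to first treatment but adds a test against the end date. For the same-month case it reads "If the imputed start date that is after the specified end date, then use the 1st of the month". Equivalent tests follow for the year-only and wholly unknown cases. SAP 6.1.4 has no such test, and SAP 6.1.5 (Data derivation rules) is marked as not applicable.

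**The concern.** The definition of prior depends only on the start date. If that date is imputed to first treatment, the medicine can no longer be prior, even when the recorded stop date shows that it was finished before dosing. It cannot be concomitant either, because nothing overlaps a treatment period. The sentence on missing starts does not help, since it covers only stops that are unknown or after first treatment.

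At stake is the completeness of the prior-medication summary. Exclusion criterion 11 in Protocol 5.2 restricts medicines, including enzyme inhibitors or inducers and gastric pH modifiers, for 2 weeks (4 weeks for inducers) or 5 half-lives "before the first administration of study medication and during the clinical part of the study, unless required to treat an AE". A reader would look in that summary for recently stopped medicines. Screening runs from Day -28 to Day -2, so a medicine used in that window can easily share the calendar month of first dose, which is one of the conditions for the gap. The error runs one way: the table can only under-report prior use.

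**Working it through.** The plan gives no figure to reproduce, so the check applies the rules as written.

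**Notation.** F is the date of first treatment, S* the start date after imputation, and E the stop date (known or imputed).

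**Rules, from SAP 6.1.4.**

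1. In the three situations above, S* = F.
2. Prior requires S* < F.
3. Concomitant requires the interval from S* to E to share at least one day with a treatment period, which needs S* ≤ E.
4. The missing-start sentence applies only if E is unknown or E > F.

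**General result.** Take S* = F and E < F. Rule 2 fails because F < F is false. Rule 3 fails because S* > E, so there is no duration to overlap anything. Rule 4 does not apply. The record is in neither class. This follows from the rules alone and needs no assumption about the data.

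**Worked records.** Assumptions: F = 20 March 2024 (illustrative), and Treatment Period 1 starts on Day -1, as in SAP Table 5-1.

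| Recorded start | Recorded stop | S* | E | Prior | Concomitant |
|---|---|---|---|---|---|
| unknown | 10 Mar 2024 | 20 Mar 2024 | 10 Mar 2024 | no | no |
| Mar 2024 | 10 Mar 2024 | 20 Mar 2024 | 10 Mar 2024 | no | no |
| 2024 | 15 Jan 2024 | 20 Mar 2024 | 15 Jan 2024 | no | no |
| 2024 | Jan 2024 | 20 Mar 2024 | 31 Jan 2024 | no | no |
| unknown | 2023 | 20 Mar 2024 | 31 Dec 2023 | no | no |
| Mar 2024 | 19 Mar 2024 (Day -1) | 20 Mar 2024 | 19 Mar 2024 | no | no |

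In the second row, stop minus start is 10 - 20 = -10 days.

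The last row depends on programming. A program that compared only the endpoints with Treatment Period 1, without requiring S* ≤ E, could call it concomitant. It would still not be prior.

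**Controls, to mark the edge of the problem.**

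| Recorded start | Recorded stop | S* | E | Prior | Concomitant |
|---|---|---|---|---|---|
| Feb 2024 | 10 Mar 2024 | 1 Feb 2024 | 10 Mar 2024 | yes | no |
| 2023 | 10 Mar 2024 | 1 Jan 2023 | 10 Mar 2024 | yes | no |
| 5 Mar 2024 | 10 Mar 2024 | 5 Mar 2024 | 10 Mar 2024 | yes | no |
| Mar 2024 | Mar 2024 | 20 Mar 2024 | 31 Mar 2024 | no | yes |
| Mar 2024 | 20 Mar 2024 (Day 1) | 20 Mar 2024 | 20 Mar 2024 | no | yes |
| unknown | unknown | 20 Mar 2024 | missing | no | yes |

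Every control falls into a class. The gap therefore needs both conditions together: a start imputed to F, and a stop before F.

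**With the stop-date check added** (assumed Screening date 25 February 2024), the six affected records become, in order:

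- 25 Feb to 10 Mar 2024
- 1 to 10 Mar 2024
- 1 to 15 Jan 2024
- 1 to 31 Jan 2024
- 1 Jan to 31 Dec 2023
- 1 to 19 Mar 2024

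All six are prior. The last is also concomitant, because Day -1 belongs to Treatment Period 1.

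**The case against.** The strongest reply is that nothing important depends on this table.

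- **Listings.** SAP 5.1 requires a complete set of listings of all documented and calculated data, so the records remain visible.
- **Eligibility.** Criterion 11 is policed elsewhere. Eligibility is verified at Screening and Day -1, and concomitant medication is reviewed from Screening onwards. SAP 5.1.1.2 and 6.1.2 have deviation classes for eligibility and for prohibited or disallowed medication, reviewed at data meetings.
- **Status of the table.** Prior and concomitant medications sit in the SAP appendix of non-key analyses.
- **Intent.** It can be guessed: if a missing start with a later stop is concomitant, a missing start with an earlier stop was presumably meant to be prior.

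The first three points stand and set the size of the finding. The fourth explains the omission but does not cure it. The text tells the programmer to impute first and classify afterwards, and followed literally that gives the wrong class.

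A reader might infer three stronger things that the documents do not support:

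- **That the Part A PK results are at risk.** The Part A models in SAP 5.4.2 contain sequence, participant, period, formulation and, where relevant, gastric status. The Pharmacokinetic Set depends on important deviations affecting PK. Neither uses the prior/concomitant flag.
- **That all partial start dates are mishandled.** The controls show that they are not.
- **That a large share of records is lost.** Every record meeting both conditions is lost, but that is true by construction and says nothing about how many there will be.

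**Conclusion.** The concern holds on the text as written. SAP 6.1.4 gives a wrong result for medicines whose start is imputed to first treatment and whose known or imputed stop is earlier: they appear in neither the prior nor the concomitant summary, with a start date after the stop date. The SAP already guards against this for adverse events, so it reads as a drafting omission.

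It is minor. It affects a descriptive table only and changes no PK estimate, confidence interval or analysis set. The number of records affected is unknown, because the documents do not say how many medication dates will be partial or missing. The general result rests only on the wording of 6.1.4; the calendar dates in the working are illustrative.

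**What to change.** Add two rules to SAP 6.1.4:

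1. A medication with a stop date before the first treatment is always classified as prior.
2. If the imputed start date is after the stop date, replace it with the 1st of the month (month and year known), January 1 of the known year (only the year known), or January 1 of the stop year (start unknown). Use the Screening date instead if that is later and not after the stop date.

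The first rule alone repairs the classification. The second removes impossible dates, and with them negative durations and misleading relative days. It also brings the section into line with 5.5.2. The Screening clause affects only the imputed start date; each affected record is prior with or without it.

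The cost is two sentences in the SAP and a few lines of code. Records that are already classified correctly do not change, and no data collection or clinical procedure is involved.

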6.1.5 Data derivation rules

Not applicable.

6.1.6 AEs of Special Interest

AE of special interest are:

- Hy's Law: Potential Hy's Law is defined as ≥ 3 xULN, ALT or AST with coexisting ≥ 2 xULN total bilirubin in the absence of ≥ 2 xULN ALP, with no alternative explanation for the biochemical abnormality (ie, without waiting for any additional etiologic investigations to have been concluded).
- Hypersensitivity reactions (such as rash, angioedema, or anaphylaxis).

A listing will be produced of Potential Hy's Law for the SS for Part A by treatment and for Part B by dose level and ethnic group.

A listing will be produced for Hypersensitivity reactions for the SS for Part A by formulation and for Part B by dose level and participant group using the following search strategy: Standardized MedDRA Queries (SMQ)='Hypersensitivity' (Broad) AND SMQ=Anaphylactic reaction (Broad).

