## **2.3        Benefit/risk assessment**

This study will not provide any benefit to the study population, ie, healthy study participants, instead it will provide relevant pharmacological and clinical safety information to support UCB0599 new formulation development as well as to support the further development of UCB0599 in Japanese and Chinese populations. In Phase 1 development of UCB0599, 5 studies (UP0030, TM0017, UP0023, UP0077, and UP0078) demonstrated that UCB0599 has acceptable safety, PK, and tolerability profiles for further clinical development.

Drug hypersensitivity is an important identified risk for UCB0599. Cardiac effects are an important potential risk based on nonclinical data. Overall, the majority of treatment-emergent adverse events (TEAEs) seen in the Phase 1 and Phase 2 studies were mild or moderate in intensity and resolved. In UP0030, 2 events of hypersensitivity were reported. An additional 2 events of hypersensitivity occurred in study participants who received UCB0599 in UP0077. A causal relationship between the reported events of drug hypersensitivity and UCB0599 is considered plausible. There have been no reports of anaphylaxis in the UCB0599 clinical program.

Based on the results of UP0030, drug hypersensitivity and symptoms commonly associated with anaphylaxis and angioedema have been considered adverse events of special interest (AESI) and an important identified risk, based on reasonable clinical judgment. To minimize the risks for study participants, the study team at UCB and the contract research organization (CRO) will continue to systematically review safety data and UCB0599 exposure data. The site will be informed and trained appropriately about the risk of a hypersensitivity reaction (such as rash, angioedema, or anaphylaxis) and the actions that need to be taken in case of a hypersensitivity reaction. The participant will be informed by the Investigator during the consent procedure about the risk of a hypersensitivity reaction and other important potential risks for UCB0599. Risk

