### **8.3.6 AESIs**

An AESI is any AE that a regulatory authority has mandated be reported on an expedited basis, regardless of the seriousness, expectedness, or relatedness of the AE to the administration of a UCB product/compound.

For UCB0599, the following events require immediate reporting (within 24 hours regardless of seriousness) to UCB:

- Hy's Law
  - Potential Hy's Law, defined as  $\geq 3 \times \text{ULN}$ , ALT or AST with coexisting  $\geq 2 \times \text{ULN}$  total bilirubin in the absence of  $\geq 2 \times \text{ULN}$  ALP, with no alternative explanation for the biochemical abnormality (ie, without waiting for any additional etiologic investigations to have been concluded). Follow up information should be reported if an alternative etiology is identified during investigation and monitoring of the participant.
- Hypersensitivity reactions (such as rash, angioedema, or anaphylaxis)

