5.2 Participant Dispositions

Participant screening and primary reason for screen failure will be summarized using the ASPS, separately for Part A and Part B. The summaries will include the following:

- Number of participants screened
- Number and proportion of participants rescreened
- Number and proportion of participants with screen failures (Not counting successfully rescreened participants)
- Number and proportion of screen failures by primary reason for screen failure (Based on the later screening visit)

By-participant listings of rescreened participants will be presented using the ASPS.

Participant disposition will be summarized using the ASPS, separately for Part A and Part B. Each summary will include the following:

- Date of first screening visit
- Date of last visit for last participant
- Number of participants screened
- Number of participants in each analysis set, by treatment sequence (according to randomized treatment).

Disposition of analysis sets will be tabulated using the ASPS, separately for Part A and Part B. Each table will present the total number of participants in the ASPS, as well as the number and percentage of participants in each analysis set by treatment sequence.

Study completion/discontinuation and primary reason for discontinuation will be summarized using the RS, separately for Part A and Part B. Each table will present the following, by treatment sequence:

- Number and percentage of participants that started the study
- Number and percentage of participants completing the study
- Number and percentage of participants discontinuing the study
- Number and percentage of participants discontinuing the study by primary reason for discontinuation.
- Part A only:
 - Number and percentage of participants that started substudy 1 and substudy 2
 - Number and percentage of participants completing substudy 1 and substudy 2
 - Number and percentage of participants discontinuing substudy 1 and substudy 2

Participants that started the study are defined as participants that were randomized. Participants completing the study are those participants completing the SFU visit AND who did not discontinue dosing or withdraw from the study for any reason before the SFU.

Participants that started substudy 1 and substudy 2 are defined as participants who started treatment period 1 and 4, respectively. Participants completing the substudy 1 and substudy 2 are those participants completing Washout period 3 and 6, respectively.

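### SAP 6.1.6 joins the two hypersensitivity queries with AND, so the dedicated AESI listing, programmed as written, omits any event that only one query finds

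*SAP*

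**What the plan says.** SAP 6.1.6 names two AESIs, potential Hy's Law and hypersensitivity reactions, and plans a listing for each on the Safety Set. The hypersensitivity listing is to be produced with this search: "Standardized MedDRA Queries (SMQ)='Hypersensitivity' (Broad) AND SMQ=Anaphylactic reaction (Broad"). The part at issue is how the second query is joined to the first: "AND SMQ=Anaphylactic reaction (Broad").

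The AESI itself is defined more widely. Protocol 8.3.6 has "Hypersensitivity reactions (such as rash, angioedema, or anaphylaxis"), and SAP 6.1.6 repeats the definition. The examples are joined by *or*, and no anaphylactic feature is required.

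Protocol 2.3 gives the background:
- "Drug hypersensitivity is an important identified risk for UCB0599".
- "In UP0030, 2 events of hypersensitivity were reported", and "An additional 2 events of hypersensitivity occurred in study participants who received UCB0599 in UP0077".
- "There have been no reports of anaphylaxis in the UCB0599 clinical program".

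Two other parts of the SAP bear on the point. SAP 5.5.2 plans a by-participant listing of all AEs in which AESIs are flagged, but does not say how the flag is derived. SAP 6.1.5, on data derivation rules, is marked not applicable.

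**The concern.** In a search strategy a capitalised AND is an operator: an event is selected only if it satisfies both queries. A programmer following SAP 6.1.6 to the letter would therefore drop any event found by the Hypersensitivity query alone, and any found by the Anaphylactic reaction query alone. The listing would then be narrower than the definition printed just above it.

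At stake is the completeness of the one output dedicated to hypersensitivity. A reader of the study report would reasonably take a listing headed as hypersensitivity reactions to hold all of them. For a risk that the sponsor already treats as identified and important, that reader should not have to search the full AE listing to find out whether something was left out.

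**Working it through.** The plan states no figure here, so there is none to reproduce. The check is set logic, followed by a comparison of the relevant sections.

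**Set logic.** Let H be the events in SMQ Hypersensitivity (Broad) and A the events in SMQ Anaphylactic reaction (Broad).

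| Event is in | Listed under AND | Listed under OR |
|---|---|---|
| both H and A | yes | yes |
| H only | no | yes |
| A only | no | yes |
| neither | no | no |

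- Number listed under AND: |H ∩ A|, which is at most min(|H|, |A|).
- Number listed under OR: |H ∪ A| = |H| + |A| − |H ∩ A|, which is at least max(|H|, |A|).
- Number omitted by AND: |H ∪ A| − |H ∩ A| = |H| + |A| − 2|H ∩ A|.

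The number omitted is zero only if the two queries pick out exactly the same events in this trial. If one query's events lay wholly inside the other's, AND would reduce the listing to the smaller query and the larger one would add nothing. |H|, |A| and their overlap are not known, so the formula cannot be filled in.

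**Does the SAP mean a conjunction by AND?** Another capitalised AND in the SAP, in the definition of completers in 5.2, reads "completing the SFU visit AND who did not discontinue dosing or withdraw from the study for any reason before the SFU". There both conditions are plainly required. Nothing in 6.1.6 says that the two queries are to be pooled or listed separately, and 6.1.5 supplies no derivation rule that would settle it.

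**Does the intersection match the AESI?** It does not. Protocol 8.3.6 and SAP 6.1.6 treat the example reactions as alternatives. Protocol 2.3 describes the AESI as drug hypersensitivity together with symptoms typical of anaphylaxis and angioedema, so it has two components, each to be captured. Protocol 8.3.6.1 makes hypersensitivity reactions reportable whatever their seriousness, expectedness or relatedness. A union of the two queries fits all of this; an intersection does not.

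**What uses the search?**
- The 6.1.6 hypersensitivity listing: yes, by definition.
- The AESI flag in the general AE listing (SAP 5.5.2): not stated.
- The TEAE incidence tables (SAP 5.5.2): no. They cover all TEAEs by SOC, HLT and PT, without an SMQ filter.
- The listing of all AEs (SAP 5.5.2): no. Every event appears whether flagged or not.
- The hypersensitivity stopping criteria (Protocol 7.1.4): no. They rest on medical judgement, relatedness and CTCAE grade.
- Safety committee review (Protocol 9.8, SAP 5.8): neither section ties it to this search.

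**The case against.** The best defence is that AND is loose wording for running both queries, and that the definition in the same section shows a union was meant. That may well be the intent. But the SAP does not say so, its wording in 5.2 points the other way, and a specification should not depend on the programmer guessing. If a union was meant, the text should say OR; if an intersection was meant, it conflicts with the definition. The sentence needs changing in either case.

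The second defence is that little depends on the search, and this largely stands. Investigators must report every hypersensitivity reaction to the sponsor within 24 hours (Protocol 8.3.6), all AEs are listed, and the general AE listing flags AESIs. The 6.1.6 listing is therefore not the only output that identifies these events, although it is the only one dedicated to hypersensitivity. If the flag were built from the same search it would share the gap, but the event itself would still be in the listing.

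Three stronger readings are tempting, and the documents support none of them:
- *A distorted incidence.* Part B has 8 participants on active drug per dose and origin, so one event is 1/8 = 12.5% of such a group. A reader might infer that one missed event shifts observed incidence by 12.5 points. It does not: the search feeds a listing with no rate or denominator, and the planned incidence tables would still count the event, so they change by 0 points.
- *Loss of the kind of event seen so far.* The protocol cites 2 + 2 = 4 earlier hypersensitivity events and no anaphylaxis, so a reader might infer that those 4 would have been dropped. That cannot be determined. Their preferred terms are not given, nor are the SMQ term lists. A broad term query is also not a diagnosis: the anaphylaxis criteria in Protocol 8.3.6.1.1.1 themselves include skin signs such as hives, itching and flushing.
- *A risk to participants during the trial.* Stopping and clinical work-up start from the suspected reaction and the investigator's judgement, not from this listing.

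**Conclusion.** The point holds as a reporting defect of limited reach. As written, the rule in SAP 6.1.6 is an intersection. It can omit events that meet the AESI definition in the same section, for a risk that the protocol calls important and identified. The effect is limited to the completeness of the dedicated hypersensitivity listing, and of the AESI flag in the general AE listing if that is derived from the same search.

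The size in events is unknown. It is |H| + |A| − 2|H ∩ A|, which may be zero in this trial and cannot be computed from the documents. The conclusion rests on one assumption, that AND is programmed literally; the SAP's wording in 5.2 supports this and nothing in the SAP contradicts it.

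**What to change.** In SAP 6.1.6:
1. Replace AND with OR, and state that the listing is the union of the two broad SMQs.
2. Add any event that the investigator reported as a hypersensitivity AESI, whether or not its coded term falls in either query, and name the data source for that designation.
3. State in SAP 5.5.2 that the AESI flag for hypersensitivity in the general AE listing follows the same rule.

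The cost is one word and two short clauses, and no analysis model or incidence table changes. The downside is that broad queries may bring a few non-specific terms into the listing. Marking which SMQ, or the investigator's report, brought each event in would let the reader discount them. The SAP (05 SEP 2023) is based on the protocol of 02 Mar 2023 and predates Amendment 1 (26 Oct 2023), so an SAP update for that amendment could carry this correction too.
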